ONCOS-102 (adenoviral vector with payload)	3 x 10 ¹¹ viral particles	Day 1, 4, 8, 15, and 19 followed by every 4 week maintenance	No DLTs	Ranki et al 2016 ³⁴
NG-350A (adenoviral vector with payload)	2 x 10 ¹² viral particles	Weekly x 4	No DLTs	Nain et al 2021 ³⁵
ORCA-010 (adenoviral vector)	1.5 x 10 ¹² viral particles	One dose	No DLTs or treatment-related Grade ≥3 AEs	Brachtlova et al 2021 ³⁶
ONCR-177 (HSV-1 vector with payload)	4 x 10 ⁸ pfu	Every 2 weeks	No DLTs or treatment-related Grade ≥3 AEs	Park et al 2021 ³⁷
IMLYGIC (HSV-1 vector with payload)	4 x 10 ⁸ pfu	Every 2 weeks	No DLTs	Hu et al 2006 ³⁸

Risks related to anti-PD-1 administration: Anti-PD-1 administration carries the risk of immune-related AEs (irAEs) in various organ systems, including the skin. Consult the current pembrolizumab or nivolumab package insert for the most current information related to administration and safety, such as AE management and dose modifications. Per the respective package inserts for nivolumab and pembrolizumab, administration of either anti-PD-1 can be associated with rash, and pruritis has been reported in melanoma patients treated with nivolumab. Given lerapolturev's mechanism of action, and the monotherapy safety profile observed in melanoma participants treated to date, it is possible that concurrent use of lerapolturev with anti-PD-1 therapy could increase the frequency or severity of cutaneous irAEs like rash or pruritis. However, review of the available safety data for participants treated with the combination of lerapolturev and anti-PD-1 therapy in this study suggests there is not an increased risk of cutaneous irAEs for

Confidential Page 44 of 109

the combination (Table 3 and Table 4). Because co-administration of lerapolturev with anti-PD-1 therapy has a theoretical risk for CRS and/or immune effector cell-associated neurotoxicity syndrome (ICANS)²⁰, this study will monitor participants for such events, and will obtain blood samples to determine the cytokine profile associated with any such events (if applicable) in order to inform treatment algorithms in subsequently treated study participants. In addition, the study will employ a safety run-in (Section 3.1.2) to establish the safety of multiple lerapolturev intratumoral injections prior to proceeding the randomized portion of the trial.

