- Grade 4, (Life-threatening): Urgent intervention indicated.
- Grade 5: Death.

The investigator should use clinical judgment in assessing the severity of events not directly experienced by the participant (eg, laboratory abnormalities).

Assessment of Causality

- The investigator is obligated to assess the relationship between study drug(s) and each occurrence of each AE/irAE/AESI/SAE and to record this determination in the eCRF. The AE must be characterized as unrelated, unlikely to be related, possibly related, probably related, or definitely related.
 - Definitely related conveys the adverse event has a timely relationship to administration of study treatment and there is no apparent, potential alternate etiology.
 - "Probably related" conveys that there are facts, evidence, and/or arguments to suggest a causal relationship, rather than a relationship cannot be ruled out.
 - "Possibly related" suggests that the association of the AE with the study treatment is unknown; however, the AE is not reasonably supported by other conditions.
 - "Unlikely to be related" suggests that only a remote connection exists between the study treatment and the AE. Other conditions, including chronic illness, progression or expression of the disease state or reaction to concomitant therapy, appear to explain the reported AE.
 - "Unrelated" is used if there is not a reasonable possibility that the study treatment caused the AE
- The investigator should use clinical judgment to determine the relationship.
- Alternative causes, such as underlying disease(s), concomitant therapy, and other
 risk factors, as well as the temporal relationship of the event to study drug(s)
 administration will be considered and investigated.
- The investigator should consult the IB during his/her assessment.
- For each AE/irAE/AESI/SAE, the investigator must document in the medical notes that he/she has reviewed the AE/irAE/AESI/SAE and has provided an assessment of causality, along with indication of the key pieces of evidence that factored into that determination.
- There may be situations in which an AESI or SAE occurs, and the investigator has
 minimal information to include in the initial report to the Sponsor/designee.
 However, it is very important that the investigator always make an
 assessment of causality for every SAE before the initial transmission of the
 AESI or SAE to the Sponsor.

Confidential Page 96 of 109

Assessment of Causality

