3.2.3.1. Missing Severity or Relationship for Adverse Events

AEs with missing severity will have the severity imputed as "Grade 3" for the AE tabulations. AEs with missing relationship to study drug will have the relationship imputed as 'Definite' for the AE tabulations if the AE started after initiation of study drugs.

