5.7.1. Adverse Events

AE will be mapped to a MedDRA version 24.0 by SOC and PT. If a participant experiences multiple events that map to a single PT, the greatest severity and strongest assessment of relation to a study drug will be assigned to the PT for the appropriate summaries. AE severity will be assessed according to the NCI CTCAE version 5. If CTCAE grading does not exist for an AE, the severity of the AE will be graded as mild (1), moderate (2), severe (3), life-threatening (4), or death (5).

AESIs will be identified within the EDC by the investigator.

The number of participants for the following groups will be summarized by treatment group and overall:

- Any TEAE
- Any TEAE related to
 - o lerapolturev

- o anti-PD-1 therapy
- Any TESAE
- Any TESAE related to
 - o lerapolturev
 - o anti-PD-1 therapy
- Any treatment-emergent lerapolturev AESIs
- Any treatment-emergent irAEs
- Any TEAE with CTCAE grade ≥ 3
- Any TEAE related to
 - o lerapolturev with CTCAE grade ≥ 3
 - o anti-PD1 therapy with CTCAE grade ≥ 3
- Any Grade 5 TEAE
- Any Grade 5 TEAE related to lerapolturev or anti-PD1 therapy

The occurrence of TEAEs and TEAEs related to lerapolturev, or anti-PD-1 therapy will be summarized by PT, SOC, and severity. Additionally, TEAEs will be summarized by PT in descending frequency. All AEs reported will be listed for individual participants showing both verbatim and PT. All AEs that occurred prior to initiation of study drugs will be excluded from the tables but will be included in the listings.

Adverse events occurring during screening due to lerapolturev-related procedures that are not standard of care (eg, PV booster) will be considered related to lerapolturev and summarized separately.

Additional analysis may be conducted to investigate rates of TEAE based on lerapolturev dose and/or schedule. Should there be a difference, we may perform additional analyses to discern whether there is a relationship between dose and occurrence of AEs.

Missing onset dates will be imputed as previously outlined in Section 3.2.3.2 as required to determine TEAE.

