11. PROPOSED TABLES, LISTINGS, AND FIGURES

Summary Tables

Accountability and Baseline Characteristics		
14.1.1.1	Participant Disposition, Screening Analysis Set	
14.1.2.1	Demographics and Baseline Characteristics, Safety Set	
14.1.4.1	Melanoma History, Safety Set	
14.1.4.2	Biomarker History, Safety Set	
14.1.4.3	Prior Systemic and Intratumoral Anti-Cancer Therapy, Safety Set	
14.1.4.4	Prior Radiotherapy for Melanoma, Safety Set	
14.1.4.5	Prior Procedures, Safety Set	
14.1.4.6	Concomitant Medications, Safety Set	
14.1.4.7	Concomitant Procedures, Safety Set	
14.1.4.8	Subsequent Anti-Melanoma Treatment, Safety Set	
14.1.5.1	Summary of Study Drug Exposure, Safety Set	
Efficacy		
14.2.1.1	Summary of Best Overall Tumor Response Based on RECIST 1.1 Criteria,	
	Efficacy Set	
14.2.2.1	Summary of Overall Survival, Efficacy Set	
14.2.3.1	Summary of Progression Free Survival, Efficacy Set	
Safety		
14.3.1.1	Overall Summary of Treatment-Emergent Adverse Events, Safety Set	
14.3.1.2	Treatment-Emergent Adverse Events by System Organ Class, Preferred Term, and	
14.5.1.2	Greatest Severity, Safety Set	
14.3.1.3	Treatment-Emergent Adverse Events by Preferred Term in Descending Frequency,	
17.3.1.3	Safety Set	
14.3.1.4.1	Treatment-Emergent Adverse Events Related to Lerapolturev by System Organ	
1	Class, Preferred Term, and Greatest Severity, Safety Set	
14.3.1.4.2	Treatment-Emergent Adverse Events Related to Anti-PD-1 by System Organ	
	Class, Preferred Term, and Greatest Severity, Safety Set	
14.3.1.5.1	Treatment-Emergent Adverse Events Related to Lerapolturev by Preferred Term in	
	Descending Frequency, Safety Set	
14.3.1.5.2	Treatment-Emergent Adverse Events Related to Anti-PD-1 by Preferred Term in	
	Descending Frequency, Safety Set	
14.3.2.1	Treatment-Emergent Serious Adverse Events by System Organ Class, Preferred	
	Term, and Greatest Severity, Safety Set	
14.3.2.2.1	Treatment-Emergent Serious Adverse Events Related to Lerapolturev by System	
	Organ Class, Preferred Term, and Greatest Severity, Safety Set	
14.3.2.2.2	Treatment-Emergent Serious Adverse Events Related to Anti-PD-1 by System	
	Organ Class, Preferred Term, and Greatest Severity, Safety Set	
14.3.3.1	Treatment-Emergent Lerapolturev Adverse Event of Special Interest by System	
	Organ Class, Preferred Term, and Greatest Severity, Safety Set	
14.3.3.2	Treatment-Emergent Immune Related Adverse Event by System Organ Class,	
	Preferred Term, and Greatest Severity, Safety Set	

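### The SAP's rule for repeat events of one preferred term can attach a Grade 3+ severity from one event to a relationship from another, so the related-by-severity tables can show a false attribution

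*SAP*

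**What the plan says.** SAP 5.7.1 gives one collapsing rule. Its trigger is "If a participant experiences multiple events that map to a single PT". In that case "the greatest severity and strongest assessment of relation to a study drug will be assigned to the PT for the appropriate summaries".

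The same section plans summaries that cross the two attributes: "The occurrence of TEAEs and TEAEs related to lerapolturev, or anti-PD-1 therapy will be summarized by PT, SOC, and severity". Its list of overall counts also has a row for any treatment-emergent event related to "lerapolturev with CTCAE grade ≥ 3", and a matching row for anti-PD-1.

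SAP Section 11 lists the outputs. Table 14.3.1.4.1 begins "Treatment-Emergent Adverse Events Related to Lerapolturev by System Organ" and continues with class, preferred term and greatest severity. Table 14.3.1.4.2 is the anti-PD-1 counterpart, and 14.3.2.2.1 and 14.3.2.2.2 repeat the layout for serious events.

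Protocol 9.2 has causality judged event by event, on five levels: "The AE must be characterized as unrelated, unlikely to be related, possibly related, probably related, or definitely related". Protocol 8.5.3 asks for the maximum grade of each event per participant, and for a separate tabulation of events at least possibly related to lerapolturev. It does not say how grade and relationship combine across repeat events. Protocol 8.5 lets the SAP prevail where the two differ.

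On missing values, SAP 3.2.3.1 says "AEs with missing relationship to study drug will have the relationship imputed as" Definite when the event began after study drugs were started. It sets missing severity to Grade 3.

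**The concern.** The rule takes two maxima separately over all of a participant's events in a PT. That is harmless in a table showing only severity or only relationship. It is not harmless in a table that reports both, because the reported pair may describe no event that took place.

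The phrase about relation to a study drug, in the singular and without naming the drug, adds a second ambiguity. The tables are specific to lerapolturev or to anti-PD-1, while the rule is not. Even if the relationship is taken separately for each drug, the severity is still the maximum over all events in the PT, whichever drug they were attributed to.

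What is at stake is the PT-level attribution of severe events, chiefly in the combination arm. Protocol 1.3.1 says that lerapolturev given with anti-PD-1 could make rash or pruritus more frequent or more severe, and notes that "pruritis has been reported in melanoma patients treated with nivolumab". For such terms a reader will want to know which drug a severe event was attributed to.

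**Working it through.** The plan gives no figure for this point, so there is none to reproduce. The check applies the rule to small examples, sizes one false cell, and then sets a ceiling from the protocol's own data.

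**1. The rule against selecting related events first**

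The examples are hypothetical. Related means at least possibly related.

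| One participant's events in one PT | SAP rule read literally | Select related events first |
|---|---|---|
| Fatigue Grade 3, unrelated; fatigue Grade 1, possibly related to lerapolturev | max grade = 3, max relationship = possible: lerapolturev-related Grade 3 | related set = {Grade 1}: lerapolturev-related Grade 1 |
| Arm 2: pruritus Grade 3, related to anti-PD-1 only; pruritus Grade 1, related to lerapolturev only | Grade 3 in both drugs' tables | Grade 1 for lerapolturev, Grade 3 for anti-PD-1 |
| Fatigue Grade 3, unrelated; fatigue Grade 1, relationship missing and imputed as Definite | related Grade 3 | related Grade 1 |

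In the second row the anti-PD-1 entry is right under both methods; only the lerapolturev entry is wrong. In the third row the imputation feeds the collapsing rule, and selecting first keeps the imputed relationship with its own event.

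**2. Size of one false cell in a QW arm**

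SAP 3.1 expects n = 15 per QW arm. The exact (Clopper-Pearson) limits for x out of n are the 2.5% quantile of Beta(x, n − x + 1) and the 97.5% quantile of Beta(x + 1, n − x).

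- x = 0: 0/15 = 0%. Lower limit 0; upper limit 1 − 0.025^(1/15) = 21.8%.
- x = 1: 1/15 = 6.7%. Lower limit 1 − 0.975^(1/15) = 0.2%; upper limit 31.9%.

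**3. Ceiling from Protocol Table 3 (cutoff 10 December 2021)**

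A false lerapolturev-related Grade 3 or 4 entry requires a participant who has both a Grade 3 or 4 event and a lerapolturev-related event. The number of such participants cannot exceed the smaller of the two counts.

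| Group | Any Grade 3 or 4 | Any lerapolturev-related | Ceiling | Reported related Grade 3 or 4 |
|---|---|---|---|---|
| Safety run-in | 2/6 | 4/6 | 2/6 | 0/6 |
| Arm 1 | 0/5 | 1/5 | 0/5 | 0/5 |
| Arm 2 | 1/6 | 1/6 | 1/6 | 0/6 |
| All, before crossover | 3/17 | 6/17 | 2 + 0 + 1 = 3/17 (17.6%) | 0/17 |
| After crossover | 1/7 | 2/7 | 1/7 | 0/7 |

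This is a ceiling and not an estimate. It would be reached only if every one of these participants had a severe event and a related milder event under the same PT. The documents do not report that overlap. Protocol 1.2.2.2 adds that no Grade 3 or higher event occurred in more than one participant, so a single PT row could hold at most one such case in those data.

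**The case against.** **The wording allows a harmless reading.** The rule applies to the appropriate summaries. That can mean severity for severity tables and relationship for relationship tables. The titles in Section 11 describe related events by greatest severity, which suggests filtering to related events first, and Protocol 8.5.3 also separates related events from all events. An experienced programmer may well do this. That much stands. But the SAP never states the order, the harmless reading leaves the crossed tables undefined, and SAP Section 5 has outputs checked for consistency with the plan. A validator following the sentence literally would accept the wrong cell.

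**The overall rows are probably safe.** A row counting participants with any related event of Grade 3 or higher is most naturally built from single events meeting both conditions. This stands. A reader might infer that the rule overturns the protocol's statement that related events have been only Grade 1 or 2; the documents do not support that. The likelier outcome is a PT table that disagrees with the overall row.

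**No severe event is invented.** A reader might take the tables to show Grade 3+ events that never happened. They would not: the event occurred, and only the attribution is wrong. The event-level listing (16.2.7.1) would reveal it.

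**The primary safety endpoint is not defined by attribution.** SAP Section 2 and Protocol 2.1 define it as frequency and severity of treatment-emergent events. Severity tables regardless of attribution are correct under the rule. Dose-limiting toxicity is defined on individual events in Protocol 3.1.4 and does not use these tables.

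**It may be rare.** In Protocol Table 4, every lerapolturev-related PT except fatigue occurs in at most one participant per column. Missing relationships should also be few, since Protocol 9.2 obliges the investigator to judge every event. Safety data follow treatment at the time of assessment, so events before crossover stay in the monotherapy columns. All of this limits the consequence; none of it corrects the rule.

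**Conclusion.** The rule is wrong as written, with minor to moderate consequence. Applied literally, it reports a severe event that was unrelated, or related only to the other drug, as related to the drug in the table title whenever a milder event of the same PT was judged related to that drug. Four PT-level tables are exposed.

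The conclusion rests on a literal reading of SAP 5.7.1, and the false cell arises only where one participant has at least two events of one PT that differ in both grade and attribution. The error makes the drug look more toxic, never less. Each case adds one participant to a PT row: 1/15 in place of 0/15 in a QW arm. How often this would happen cannot be worked out from the documents.

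The missing-relationship rule in SAP 3.2.3.1 is a separate, secondary point. It does not say that the relationship is imputed per drug, or that the relevant start is the first dose of that drug. It matters here because one imputed relationship can make a whole PT related at its highest grade.

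**What to change.** Replace the collapsing sentence in SAP 5.7.1 with:

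> For each related-to-X table, first select TEAEs at least possibly related to drug X, then take the greatest severity among those events within participant and PT. Overall severity tables use all TEAEs. The related Grade ≥ 3 rows count participants with a single TEAE meeting both conditions.

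Here X is lerapolturev or anti-PD-1, each handled separately. The serious-event tables follow the same order within serious TEAEs.

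As a secondary clarification in SAP 3.2.3.1, impute a missing relationship separately for each drug, and only for events starting on or after the first dose of that drug.

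The cost is a few sentences of SAP wording and a change in the order of one programming step. No new data are needed.

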3.2.6. Definitions and Terminology

Age

Age is age at informed consent and is as captured on the eCRF.

CONFIDENTIAL Page 19 19 November 2024

Baseline Value

For purposes of analysis, the baseline value is defined as the last non-missing value obtained prior to initiation of study drug.

Cycle 1, Day 1 (Baseline)

Cycle 1, Day 1 is the earliest day that study drug is initiated.

Study Day

Study Day is defined relative to Baseline (Cycle 1, Day 1). Thus, the study day of an event is calculated as:

Study Day = event date – date of Cycle 1, Day 1 (+ 1, if event date \geq date of Cycle 1, Day 1).

Study Visit

Study Visit is the nominal visit as recorded on the eCRF.

Change from Baseline

Change from baseline for a given endpoint is defined as the Study Day X value minus the Baseline Value.

Days on Study

Days on study is the number of days from Cycle 1, Day 1 to the date of study completion as recorded on the End of Study eCRF page.

Adverse Event (AE)

An AE is any untoward medical occurrence in a patient or clinical study participant, temporally associated with the use of study drug(s), whether or not considered related to the study drug(s). An AE can therefore be any unfavorable and unintended sign (including an abnormal laboratory finding), symptom, or disease (new or exacerbated) temporally associated with the use of study drug(s).

Treatment-emergent Adverse Event (TEAE)

A TEAE is an AE that occurred during the study on or after the initiation of study drug through 30 days after last dose of study drugs. Additionally, it is assumed that an AE which was reported to have started on Cycle 1, Day 1 without an associated onset time occurred on or after initiation of study drug. Treatment-emergent serious adverse events (TESAEs) are collected through 90 days post last dose of study drug.

Adverse Event of Special Interest (AESI)

Any AE (serious or non-serious) of scientific and medical concern for which ongoing monitoring and communication by the investigator to the Sponsor or designee may be appropriate. Such events may require further investigation to characterize and understand them.

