Because lerapolturev is an immunotherapeutic administered by intratumoral injection, AESIs fall into 2 categories: (1) AEs related to lerapolturev administration (ie, injection site reaction [ISR]), and (2) AEs related to cytokine release syndrome [CRS] and immune effector cell-associated neurotoxicity syndrome [ICANS], which can occur when the body's immune cells release a bolus of inflammatory cytokines in response to an immunotherapy.

AESIs are collected through 90 days post last dose of study drug.

Immune-Related Adverse Events (irAEs)

Any adverse event affecting an organ system through an autoimmune or inflammatory mechanism, whereby the immune system is acting against normal tissue. The list of terms to identify irAEs is as

follows: (1) high level term (HLT): Colitis (excl infective); (2) HLT: Lower respiratory tract inflammatory and immunologic conditions; (3) HLT: Hepatocellular damage and hepatitis NEC; (4) HLT: Hypothalamic and pituitary disorders NEC; (5) HLT: Adrenal cortical hypofunctions; (6) HLT: Diabetes mellitus (incl subtypes); (7) HLT: Nephritis NEC; (8) HLT: Encephalitis NEC; (9) Preferred term (PT): Toxic epidermal necrolysis; (10) PT: Severe cutaneous adverse reaction; (11) PT: SJS-TEN overlap; (12) PT: Stevens-Johnson syndrome. Recommendations for study drug management in the event of an irAE are described in Protocol Section 5.5.

irAEs are collected through 90 days post last dose of study drug.

Concomitant Medications

Concomitant medications are those medications taken on or after the initiation of study drugs through 30 days post last dose of study drug. This definition includes medications started prior to initiation of study drugs and continuing concomitantly with study drugs.

Prior Medications

Prior medications are those medications taken and discontinued prior to initiation of study drugs.

Complete Response (CR)

A CR is defined by:

- disappearance of all target lesions AND
- disappearance of all non-target lesions AND
- all lymph nodes must be non-pathological in size (< 10 mm short axis) AND
- no appearance of new unequivocal lesions.

Partial Response (PR)

A PR is defined by:

- \geq 30% decrease in the sum of diameters of target lesions, taking as reference the baseline sum diameters AND
- non-CR / non-PD or not evaluated non-target lesions AND
- no appearance of new unequivocal lesions.

Stable Disease (SD)

Stable disease (SD) is defined by:

- non-PR / non-PD of target lesions AND

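### Serious events with onset 31–90 days after last dose count as TESAEs but not as TEAEs, so the overview table's Any TEAE, Grade ≥3 and Grade 5 rows can disagree with its serious-event rows

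*SAP*

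**What the plan says.** SAP 3.2.6 defines a TEAE as an adverse event occurring "on or after the initiation of study drug through 30 days after last dose of study drugs". The same paragraph adds: "Treatment-emergent serious adverse events (TESAEs) are collected through 90 days post last dose of study drug". The next definitions give two further classes the longer period: "AESIs are collected through 90 days post last dose of study drug" and "irAEs are collected through 90 days post last dose of study drug".

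SAP 5.7.1 lists the overview rows. Some are built on TESAE (for example "Any TESAE related to" each study drug), two cover AESIs and irAEs, and the severity and death rows are built on TEAE: "Any TEAE with CTCAE grade ≥ 3", any Grade 5 TEAE, and "Any Grade 5 TEAE related to lerapolturev or anti-PD1 therapy". SAP section 11 names the table that the list matches, 14.3.1.1: "Overall Summary of Treatment-Emergent Adverse Events, Safety Set". It also plans serious-event tables by greatest severity (14.3.2.1), with related versions for each drug (14.3.2.2.1 and 14.3.2.2.2).

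In the protocol, section 8.5.3 gives 30 days for treatment-emergent events and no separate period for serious ones. Table 8 in section 7.3.1 collects all serious events, AESIs and irAEs to 90 days and other events to 30. Section 9.2 makes any adverse event that results in death a serious one. Section 8.5 lets the SAP prevail where the two documents differ.

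**The concern.** A fatal adverse event is by definition serious, so a reader expects the fatal events in an overview table to be a subset of the serious ones, and the serious ones a subset of all treatment-emergent ones. With a 30-day window on one set of rows and a 90-day window on another, neither relation is guaranteed.

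Frequency and severity of treatment-emergent events is a primary endpoint. Protocol Table 3, the December 2021 safety summary, already uses this layout, with rows for Grade 5 and related Grade 5 events, and protocol section 1.2.2.2 draws on it to state that there were no Grade 5 events. The final table will be read in the same way. On the literal text the omission runs one way only: it can lower the severe and fatal counts but never raise them.

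**Working it through.** The SAP gives no figure to reproduce. The check is to apply its definitions to a test case: a drug-related fatal adverse event, classified by day of onset after last dose.

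Three readings of SAP 3.2.6 are possible:
- A, literal: TEAE to Day 30, TESAE to Day 90.
- B, TESAE as a strict subset of TEAE: both to Day 30, as in protocol 8.5.3.
- C, serious events counted as TEAEs to Day 90. The SAP does not state this.

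| Onset after last dose | A: TESAE rows | A: TEAE, Grade ≥3, Grade 5 rows | B: TESAE rows | B: TEAE, Grade ≥3, Grade 5 rows | C: TESAE rows | C: TEAE, Grade ≥3, Grade 5 rows |
|---|---|---|---|---|---|---|
| Day 10 or 30 | in | in | in | in | in | in |
| Day 31, 60 or 90 | in | out | out | out | in | in |
| Day 91 | out | out | out | out | out | out |

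Length of the mismatch under A: 90 − 30 = 60 days. Under B the rows agree, but only because a serious event that the protocol requires to be collected drops out of the TESAE tables as well. Only C puts the event in every row where a reader would look for it.

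**Can Any TESAE exceed Any TEAE?** The rows count participants. Let a be those with both a TEAE and a TESAE, b those with a TEAE only, and c those whose only qualifying event is a serious one on Days 31–90. Any TEAE = a + b and Any TESAE = a + c, so the serious row is larger when c > b. This is possible under A but needs unusual data. In protocol Table 3, 10 of 17 participants had an adverse event and 1 had a serious one. Taking that one to be among the 10, b = 10 − 1 = 9, and c would have to exceed 9.

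**Which rows are most exposed?** A participant with a late fatal event has often had some earlier TEAE and is then already in the Any TEAE row, and perhaps in the Grade ≥3 row. The Grade 5 rows have no such cover, because the fatal event is the only one that could put the participant there.

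**Size, as an illustration.** Assume one related fatal event with onset on Days 31–90 in a QW arm of the planned 15 (SAP 3.1):
- as defined under A: 0/15 = 0%, exact (Clopper-Pearson) 95% CI 0% to 21.8%;
- with serious events counted to Day 90: 1/15 = 6.7%, exact 95% CI 0.2% to 31.9%.

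**The case against.** The strongest reply is that the SAP sentence on serious events speaks of collection, not of an analysis window. Because it sits inside the TEAE definition, it may be meant to extend that definition for serious events (reading C). Alternatively, protocol 8.5.3 suggests that TESAEs are simply the serious TEAEs to Day 30 (reading B). It is true that the analysis window is not stated separately and that the intent is uncertain. But the SAP does not state reading C, and reading B only moves the omission into the TESAE tables. The text has to choose.

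Three stronger inferences are tempting, and the documents do not support them.
- A reader might infer that any related death dated Days 31–90 is missed. The definition turns on when the adverse event occurred, and SAP 5.7.1 imputes onset dates to decide TEAE status. A fatal event with onset by Day 30 and death on, say, Day 60 can still be a Grade 5 TEAE.
- A reader might infer that the Grade 5 rows cover only a third of the period at risk. They cover the whole treatment period plus 30 days; what is missing is 60 days at the end.
- A reader might infer that deaths are concealed. Under the literal reading the event is in the TESAE rows of the same overview table and in Table 14.3.2.1 and, if related, the matching 14.3.2.2 table. It is also in the listing of all adverse events and in disposition, which gives the reason for death.

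It is also fair to say that few events should fall in the gap. Protocol 7.3.1 keeps progression out of adverse-event reporting, and at the December 2021 cutoff there were no Grade 5 events among 17 participants, though on the earlier dose and schedule.

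**Conclusion.** The concern holds as an internal inconsistency in the primary safety overview. Under the literal SAP definitions, a serious event with onset on Days 31–90 is counted among serious events but not among all, Grade ≥3 or Grade 5 events, so the Grade 5 rows of Table 14.3.1.1 can contradict Table 14.3.2.1. Non-serious AESIs and irAEs collected on those days have the same unclear relation to the Any TEAE and Grade ≥3 rows.

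The conclusion rests on taking TESAEs as counted through Day 90, the natural reading of a sentence that calls them treatment-emergent for that period. The documents do not say how many events will fall there. The 0/15 to 1/15 shift is conditional on one event and is not a forecast. It also ignores crossover, since SAP 5.7 assigns safety data to the treatment being received at the time. This should be corrected because the arms are small and the remedy is cheap. It is not evidence that the safety conclusions would be wrong.

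**What to change.** In SAP 3.2.6, define treatment-emergent by onset of the event, starting at first dose:
- through 90 days after last dose for serious adverse events, AESIs and irAEs;
- through 30 days after last dose for all other adverse events.

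Apply this to the Any TEAE, Grade ≥3, Grade 5 and corresponding related rows of Table 14.3.1.1, so that TESAEs are a subset of TEAEs and the Grade 5 counts agree with Table 14.3.2.1. Keep the AESI and irAE rows at 90 days whether or not the event is serious; a blanket 30-day limit on non-serious events would remove events from those rows that the SAP collects to Day 90. Footnote the windows in Table 14.3.1.1.

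The cost is one definition, one programming flag and one footnote, on data already collected. There are two drawbacks. Severe and fatal counts may be slightly less favourable. The Grade ≥3 row will also combine a 90-day window (serious events, AESIs, irAEs) with a 30-day window (other events), which is why the footnote is needed.
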